4.1.3 Analysis Windows

Defined as follows:

- Day 1 = study treatment initiation date
- Week 4: -21 / +14 days
- Weeks 8, 12, 16: +/- 14 days
- Week 22: -14 / +7 days
- Week 24: -7 days up to maximum days observed

Baseline refers to study evaluation closest to Week 0 prior to initiation of study treatment unless otherwise stated.

In the event of multiple results within a study window, the result closest to the scheduled evaluation week based on the time since study treatment initiation date will be used. Exceptions may include repeat visits for confirmation of events such as virologic failures.

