5.1 Regimens, Administration, and Duration

5.1.1 Regimens

At study entry, participants will be randomized 2:1 to oral CVC (Arm A) or oral placebo for CVC (Arm B) once a day. The study treatment will be added to the participants' pre-existing ARV regimens.

Table 5.1.1-1: Pre-existing ART Regimen and CVC or Placebo for CVC Dose

Pre-existing ART regimen	Arm A	Arm B
EFV	CVC 300 mg	Placebo for CVC 300 mg
All other ARTs	CVC 150 mg	Placebo for CVC 150 mg

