6.0 CLINICAL AND LABORATORY EVALUATIONS

6.1 Schedule of Evaluations

Table 6.1-1: Schedule of Evaluations

Evaluation	Screening	Pre-Entry	Entry	Post-Entry Evaluations (weeks, see section 6.2.3 for visit windows)						Confirmation of Suspected Virologic Failure	Confirmation of Grade ≥ 3 Toxicity	Premature Treatment Discontinuation	Premature Study Discontinuation	
				4	8	12	16	22	24					
Documentation of HIV-1	X													
Medical History	X		X											
Medication History	X		X											
Complete Physical Exam	X													
Targeted Physical Exam			X	X	X	X	X	X	X		(X) (see section 6.3.4)	X	X	
Weight	X				X			X					X	
Height	X													
Waist Circumference	X				X			X					X	
Concomitant Medications				X	X	X	X	X	X					
Study Treatment Modifications				X	X	X	X	X	X				X	
Hematology	X	X	X		X		X	X	X		(X) (see section 8.1)	X	(X) (see section 6.2.4)	

Evaluation	Screening	Pre-Entry	Entry	Post-Entry Evaluations (weeks, see section 6.2.3 for visit windows)						Confirmation of Suspected Virologic Failure	Confirmation of Grade ≥ 3 Toxicity	Premature Treatment Discontinuation	Premature Study Discontinuation	
				4	8	12	16	22	24					
Blood Chemistries	X		X	X		X			X		(X) (see section 8.1)	X	(X) (see section 6.2.4)	
Glucose (fasting)	X		X			X			X		(X) (see section 8.1)	X	(X) (see section 6.2.4)	
Insulin (fasting, real-time)	X													
Lipid Panel (fasting)	X								X		(X) (see section 8.1)	X	(X) (see section 6.2.4)	
Liver Function Tests	X		X	X		X			X		(X) (see section 8.2.1)	X	(X) (see section 6.2.4)	
HbA1C (real-time)	X								X				X	
Prothrombin Time and International Normalized Ratio			X								(X) (see section 8.2.1)		(X) (see section 6.2.4)	
hsCRP (real-time)	X													
Estimated GFR	X		X	X		X			X		(X) (see section 8.2.2)	X	(X) (see section 6.2.4)	
Pregnancy Testing	X		X (see section 6.3.5)	If suspected								If suspected		
CD4 ⁺ /CD8 ⁺		X	X			X		X	X				X	

Evaluation	Screening	Pre-Entry	Entry	Post-Entry Evaluations (weeks, see section 6.2.3 for visit windows)						Confirmation of Suspected Virologic Failure	Confirmation of Grade ≥ 3 Toxicity	Premature Treatment Discontinuation	Premature Study Discontinuation	
				4	8	12	16	22	24					
Plasma HIV-1 RNA	X		X	X		X			X	X			X	
Stored Plasma		X	X			X		X	X				X	
Stored Serum (fasting)			X			X			X				X	
Stored PBMC		X	X			X		X	X				X	
FDG-PET with CT		X							X			(X) (see section 6.2.4)		
Pharmacokinetic Studies		X		X	X	X			X					
Adherence Assessment			X	X	X	X	X	X	X				X	

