6.2.2 Entry Evaluations

Entry evaluations must occur within 60 days from the date of the pre-entry FDG-PET/CT imaging unless otherwise specified. Participant must begin treatment within 72 hours after randomization.

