6.2.3 Post-Entry Evaluations

On-Treatment Evaluations

All post-entry evaluations must be scheduled as per [section 6.1](#).

Weeks 4 through 22 have a visit window of ± 7 days. Week 24 has a visit window of -7 and +14 days.

Study Completion Evaluations

The week 24 evaluations will be the participant's final on-study visit. Participants must continue taking the study treatment until all week 24 evaluations are completed. If needed, study treatment will be extended until the week 24

evaluations are completed. It is encouraged that all week 24 evaluations occur on the same day. If evaluations cannot occur on the same day as the FDG-PET/CT imaging, evaluations must occur ± 7 days of imaging. Site personnel should notify the A5415 CMC via email ([contact]) if study treatment is anticipated to require extension past the week 24 visit window to complete the required evaluations.

Event-Driven Evaluations

Evaluations must be scheduled as per [section 8.0](#).

Confirmation of Suspected Virologic Failure

Virologic failure is defined as two consecutive plasma HIV-1 RNA levels ≥ 200 copies/mL at any visit.

If the HIV-1 RNA level is ≥ 200 copies/mL at any visit, a repeat HIV-1 RNA will be performed (per [section 6.1](#)) within 2 weeks of receipt of the result. If the Confirmation of Suspected Virologic Failure visit coincides with a regularly scheduled visit, the evaluations should be combined. If the repeat HIV-1 RNA level is ≥ 200 copies/mL, the participant will be considered to have confirmed virologic failure and the A5415 CMC must be notified via email CMC ([contact]) within 48 hours.

If a participant is confirmed to have virologic failure, the participant must return to the clinic to complete the premature treatment discontinuation evaluations as described in **section 6.2.4** and then taken off study treatment. If an evaluation is not completed at the premature treatment discontinuation visit, effort should be made to obtain the evaluation as soon as possible and within the evaluation window. The participant will be followed on study/off study treatment through completion of the study.

Confirmation of Grade ≥ 3 Toxicity

Toxicities are defined in [section 8.0](#). Evaluation of Grade ≥ 3 laboratory toxicity must follow instructions outlined in [sections 8.1](#) and [8.2](#). Only the evaluations required to assess the toxicity are required at this visit.

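### The SAP's week 24 window, counted from first dose, can miss a few valid late on-treatment scans, and the SAP has no rule that keeps them

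*SAP*

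**What the plan says.** **Time origin and windows in the SAP.** Section 4.1.3 fixes "Day 1 = study treatment initiation date". The two late windows are "Week 22: -14 / +7 days" and "Week 24: -7 days up to maximum days observed". The only selection rule is "In the event of multiple results within a study window, the result closest to the scheduled evaluation week", judged by time since first dose. It deals with several results in one window, not with one result that falls in two windows or in the wrong one.

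**Visit timing in the protocol.** The schedule in section 6.1 heads its columns "Post-Entry Evaluations (weeks, see section 6.2.3 for visit windows". Section 6.2.3 states "Week 24 has a visit window of -7 and +14 days". Section 5.1.1 places randomization at entry ("At study entry, participants will be randomized 2:1 to oral CVC (Arm A"), and section 6.2.2 adds "Participant must begin treatment within 72 hours after randomization". SAP 5.7 tabulates the gap from entry to first dose as 0, 1, 2, 3 and 4 or more days.

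**What depends on the window.** SAP 4.1.4 admits participants with at least 22 weeks on study treatment to the efficacy set and requires a baseline and week 24 scan pair for the complete-case set. SAP 7.2 imputes week 24 scans that could not be read or were not done. PET/CT is scheduled only at pre-entry and week 24. Protocol 6.2.4 adds a scan at treatment discontinuation from week 12 onward, preferably within 7 days of the last dose; those participants then have no week 24 scan.

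**The concern.** The two documents use the same lower limit of 7 days but seem to measure it from different days. A site can scan within the protocol window and the scan can still fall before the SAP's week 24 window opens. There is a second mismatch inside the SAP: the efficacy set is satisfied at 22 weeks of treatment, while the week 24 window opens at 23 weeks. A scan in that gap belongs to an efficacy-set participant but has no week 24 slot.

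At stake is the primary outcome. If a programmer applies the windows as written, an observed on-treatment reading is set aside, the value is imputed, and the participant leaves the complete-case set that serves as the check on the imputation. If the programmer does not, the choice is made outside the SAP. Weeks 4 and 22 have SAP lower limits of 21 and 14 days, against 7 in the protocol. Week 24 is generous on its upper side but has no extra room on its lower side.

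**Working it through.** **Inputs.** Week 24 = 24 × 7 = 168 days and week 22 = 22 × 7 = 154 days. Protocol visit window -7 to +14 days (6.2.3). Permitted start delay 0 to 3 days (6.2.2). SAP windows from 4.1.3; efficacy-set criterion of 22 weeks from 4.1.4. Protocol weeks are taken to run from entry; the column heading implies this, but no text states it.

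**Step 1: the windows in days.**
- Protocol week 24: 168 - 7 = 161 to 168 + 14 = 182 days after entry, which is 22 permitted days.
- SAP week 24: from 168 - 7 = 161 days after first dose, with no upper limit.
- SAP week 22: 154 - 14 = 140 to 154 + 7 = 161 days after first dose.
- Weeks 22 and 24 therefore share day 161.

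**Step 2: shift the protocol window by the start delay.** Days since first dose = days since entry - delay. A scan at entry + 161 with a 3-day delay is at 161 - 3 = 158 days, or 158/7 = 22.6 weeks. That is before 161 and inside 140 to 161.

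| Start delay (days) | Visit days in SAP week 22 only, week 24 = 168 days after first dose | Visit days in SAP week 22 only, week 24 = study Day 168 |
|---|---|---|
| 0 | 0 of 22 | 0 of 22 |
| 1 | 1 (4.5%) | 0 |
| 2 | 2 (9.1%) | 1 (4.5%) |
| 3 | 3 (13.6%) | 2 (9.1%) |

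On the second reading first dose is Day 1, so Day 168 is 167 days after first dose and the window opens one day sooner. On either reading a scan at entry + 168 is at least 165 days after first dose and is always week 24.

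**Step 3: the 22-to-23-week gap.** A participant who stops treatment on day 154 and is scanned within the preferred 7 days is scanned by day 161. Any scan on days 154 to 160 is before the window, with no start delay needed. By SAP 4.1.4 this participant is in the efficacy set.

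**Step 4: possible scale.** Assume scans spread evenly over the 22 days and 10% to 30% of participants starting late; neither is in the documents. On the first reading:
- Low end, all late starters 1 day late: 0.10 × 1/22 = 0.5%, or 0.5 of 110 participants.
- High end, all 3 days late: 0.30 × 3/22 = 4.1%, or 4.5 of 110.

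On the Day 168 reading the high end is 0.30 × 2/22 = 2.7%, or 3 of 110, and the low end is zero.

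**Step 5: effect on power.** The plan's figure first. With 50 and 25 participants, SD 0.065 and difference 0.046, the noncentrality is 0.046 / (0.065 × √(1/50 + 1/25)) = 2.89. A two-sided 5% t-test then has 81.4% power, which agrees with the stated 80%.
- Losing 4% of 75 leaves 72 and gives 79.7%.
- With 110 enrolled and the planned 20% loss, 88 are evaluable. Power is 87.2%, or 85.8% after a 4% loss.
- The ceiling for permitted delays, every participant 3 days late, leaves 64.8 of 75 and gives 75.3%. This is a bound, not an expectation.

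**The case against.** The strongest reply is that the SAP never says an early scan is dropped. Imputation is for scans that could not be read or were not done, and a readable scan at the week 24 visit is neither. A completer has only one scheduled follow-up scan, so an analyst would probably use it. The SAP's own design points the same way: supplementary set one adds participants treated for at least 12 weeks, and most of their discontinuation scans would precede day 161. Gating PET/CT strictly by 4.1.3 would discard much of what that analysis exists to add. The Analysis Implementation Plan, which is not available here, may settle it. This stands: a reader might infer that the plan treats these scans as missing, and the documents do not support so firm a statement. They support only that the windows, read literally, exclude the scans and that no stated rule brings them back.

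A reader might also infer that week 24 biomarkers are lost. That is doubtful. SAP 1.2 says immunology testing was reduced to entry and week 24 samples, which suggests that samples are chosen by visit.

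Two further points stand. The entry origin is implied, not stated, and the Day 168 reading shrinks the effect. For step 3, the intercurrent-event list in SAP 2.3.1 excludes permanent treatment discontinuation, while 4.1.4 admits anyone with 22 weeks of treatment and the exclusions in 4.1.2 do not name discontinuation. The gap exists under 4.1.4; the two statements should be reconciled.

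Finally, study drug is blinded, and nothing in the documents suggests that early-edge scans would differ by arm. The issue is lost information and unplanned discretion, not a demonstrated bias.

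**Conclusion.** The point holds as a gap in the definition of the primary-endpoint window. Read literally, SAP 4.1.3 leaves up to 3 of the 22 permitted protocol visit days outside week 24 after a permitted start delay (up to 2 on the Day 168 reading). It also leaves out discontinuation scans from day 154 to day 160 in participants who meet the 22-week criterion. This rests on protocol weeks being counted from entry.

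The practical size is likely very small. It takes a late start together with a scan at the early edge, or a stop in one particular week. Under the assumed 10% to 30% of late starters, the first route touches between none and about 4 or 5 of 110 participants and costs at most about 2 points of power. The true number cannot be found from the documents. The reason to act is that the affected readings are primary-endpoint values and the remedy costs almost nothing.

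**What to change.** In SAP 4.1.3:

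1. State that for PET/CT the week 24 value is the follow-up scan obtained at least 154 days after first dose, whether at the week 24 visit or at a discontinuation visit. This matches the 22-week criterion of the efficacy set. The earliest compliant week 24 scan, at 161 - 3 = 158 days, is covered, and no other scheduled scan competes.
2. Assign week 24 laboratory and biomarker values by nominal visit. Lowering their limit to -10 days would be worse: the window would open at day 158 and overlap week 22 on days 158 to 161, and week 22 blood is also drawn.
3. Add a rule for day 161, which now falls in both weeks 22 and 24, and state whether week 24 means 168 days after first dose or study Day 168.
4. Reconcile the treatment-discontinuation entry in SAP 2.3.1 with the efficacy-set definition in 4.1.4, so that item 1 applies to a clearly defined group.

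The cost is a few lines of SAP text and a change to the window derivation. The downside is that a few scans count at 22 to 23 weeks of exposure, which the efficacy set already accepts.

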4.1.4 Analysis Sets

Efficacy set (per-protocol set): All eligible participants who remain on study treatment for at least 22 weeks and remain on the same ART drug class during their entire study period.

Complete-case set: Efficacy set participants who have baseline-week 24 pair of PET/CT scan data.

Supplementary efficacy set one: All eligible participants in the efficacy set as well as participants who remained on study treatment for at least 12 weeks and remained on the same ART drug class during their entire study period.

Supplementary efficacy set two: All eligible participants in the efficacy set excluding participants with confirmed HIV-1 RNA > 200 copies/mL or ≥ 14 consecutive days of ART interruption at any time during the course of the study.

Safety set: All enrolled participants who initiate study treatment.

4.2 Analysis Approaches

- Descriptive summaries in Section 5 will be presented for both the Safety set and Efficacy set, unless otherwise specified.
- Summary statistics for discrete and continuous outcomes will be detailed under each report-content in Sections 5 - 9.
- All statistical tests will be two-sided with a nominal alpha level of 0.05.
 - No adjustment for multiple testing will be performed.
- Stratification will be taken into account in efficacy outcome analyses unless stated otherwise.
- No statistical comparisons across groups for baseline characteristics are planned.
- Missing data for TBR analyses will be handled using multiple imputation; sensitivity analyses will be complete case where missing data are ignored.
- Missing data for biomarker analyses will be ignored (i.e., all analyses will be complete case).

Report Contents

5 Participant Characteristics and Disposition

5.1 Screening

- 1) Table of N (%) of participants screened.
- 2) Table of N (%) of participants failed screening, with reasons for failed screening.

5.2 Accrual

- 1) Figure: Bar chart of number of accrual by month
 - o By sex
 - o By treatment arm
- 2) Table of N (%) accrual by site

5.3 CONSORT diagram

Flowchart of number of participants from screening up to analyses by treatment arms, including information on exclusions from each step.

5.4 Protocol Deviations

	Cenicriviroc Mesylate (CVC) (N=xx)	Placebo (N=xx)	Total (N=xx)
Overall Deviation	xx (xx%)	xx (xx%)	xx (xx%)
Deviation Reason Category	xx (xx%)	xx (xx%)	xx (xx%)
Reason 1	xx	xx	xx
Reason 2	xx	xx	xx
...

[All contents below will be by treatment groups, unless otherwise mentioned]

5.5 Baseline characteristics

Analysis set(s): Safety set, Efficacy set

Table 1a	Demographics
Characteristic	Summary Statistic(s)
Age	Median (Q1, Q3), and P10, P90 N (%): 45-54, 55-64, 65-74, 75+
Sex at Birth	N (%): Male, female
Gender Identity	N (%): Cisgender, transgender spectrum
Race	N (%): White, Black or African American, unknown
Ethnicity	N (%): Hispanic or Latino, Not Hispanic or Latino
BMI	Median (Q1, Q3), and P10, P90 N (%): Underweight (< 18.5), normal (18.5 – 24.9), overweight (25 – 29.9), obese (30+)

Current-use of statins at entry	N (%): Current use of statins, no current use of statins.
Statin agents	N (%): statins
eGFR	Median (Q1, Q3), and P10, P90
Table 1b	HIV Characteristics
Characteristic	Summary Statistic(s)
CD4 Count	Median (Q1, Q3), and P10, P90
CD4 %	Median (Q1, Q3), and P10, P90
HIV-1 RNA	Median (Q1, Q3), and P10, P90 N (%): < LLQ, \geq LLQ (lower limit of quantification)
ART Class at entry	N (%): INSTI and NNRTI-based, INSTI-based, NNRTI-based
ART Regimens	N (%): ARV regimens at entry
Table 1c	Cardiovascular Risk Factors
Characteristic	Summary Statistic(s)
Participants' number of cardiovascular risk factors	N (%): 1, 2, 3, 4+ CV risk factors
High-risk cardiovascular risk factors (see Protocol Section 4.1.6 for the list)	For each CV risk factor: N (%): With, without

5.6 Study status

Table	Study Status
Characteristic	Summary Statistic(s)
Study Status	N (%): completed study, prematurely discontinued study
Last Clinic Visit	N (%): No follow-up, < 12 weeks, 12 - < 24 weeks, 24+ weeks
Study Discontinuation Reasons	N (%): Reasons

5.7 Treatment status

Table 1	Treatment Status
Characteristic	Summary Statistic(s)
Treatment Status	N (%): Completed, did not start, prematurely discontinued
Days from Entry to First Dose of Treatment	N (%): 0, 1, 2, 3, 4+ days
Reasons for Treatment Discontinuation	N (%): Reasons
Week of Treatment Discontinuation	N (%): Did not start, < 12 weeks, 12 - < 24 weeks, 24+ weeks
Treatment Interruption Reason	N (%): Reason
Week of Initial Interruption	N (%): Did not start, < 12 weeks, 12 - < 24 weeks, 24+ weeks
Total Interruption Duration	N (%): 1-7, 8-14, 15+ days

6 Adverse and Targeted events (AE)

6.1 Adverse Events

Analysis set(s): Safety set

Statistics: N (%)

Listing: Public ID, AE start day, AE term, Grade, Action taken with treatment, Relationship to treatment.

- 1) Table of all new, post-entry AEs by MedDRA PT grouped by SOC (reported in ClinicalTrials.gov)
- 2) Listing of longitudinal creatinine and eGFR with creatinine-related AEs
- 3) Table/listing of SAEs by MedDRA PT grouped by SOC, excluding those related to PET/CT
- 4) Listing of all AEs related to study treatment by MedDRA PT grouped by SOC, excluding those related to PET/CT
- 5) Table/listing of all AEs related to PET/CT scan by MedDRA PT grouped by SOC

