Any AE	51 (88%)	48 (84%)	99 (86%)	27 (96%)
Nausea	10 (17%)	8 (14%)	18 (16%)	6 (21%)

Preferred Term n (%)	CVC 100 mg (N = 58)	CVC 200 mg (N = 57)	All CVC (N = 115)	EFV (N = 28)
Upper respiratory tract infection	9 (16%)	9 (16%)	18 (16%)	2 (7%)
Diarrhea	7 (12%)	10 (18%)	17 (15%)	3 (11%)
Headache	9 (16%)	7 (12%)	16 (14%)	0
Rash ^b	7 (12%)	7 (12%)	14 (12%)	5 (18%)
Fatigue	6 (10%)	8 (14%)	14 (12%)	1 (4%)
Dizziness	5 (9%)	6 (11%)	11 (10%)	8 (29%)
Nasopharyngitis	2 (3%)	8 (14%)	10 (9%)	1 (4%)
Abnormal dreams	6 (10%)	3 (5%)	9 (8%)	6 (21%)
Insomnia	0	7 (12%)	7 (6%)	4 (14%)
Lymphadenopathy	3 (5%)	4 (7%)	7 (6%)	4 (14%)
Depression	2 (3%)	1 (2%)	3 (3%)	3 (11%)
Syphilis	1 (2%)	0	1 (1%)	3 (11%)

^a Note that exposure is based on ITT population.

^b Included rash, rash maculopapular, rash pruritic, rash generalized, and rash papular.

Safety data originating from the four studies completed in 2021 (Aurora, Rollover, Tandem, and CLJC242A2101) are aligned with the current knowledge of the safety profile of CVC and are summarized below.

AURORA (Study 3152-301-002)

Full Cohort

TEAEs reported by 22% participants in the CVC group and that occurred at an incidence rate of 22% greater than in the placebo group were nausea (104 [8.8%] participants in the CVC group versus 39 [6.6%] participants in the placebo group), alanine aminotransferase increase (45 [3.8%] participants in the CVC group versus 9 [1.5%] participants in the placebo group), aspartate aminotransferase increase (38 [3.2%] participants in the CVC group versus 6 [1.0%] participants in the placebo group), and nephrolithiasis (25 [2.1%] participants in the CVC group versus 0 participants in the placebo group). CVC 150 mg once daily was, in general, well tolerated in this study, there were no treatment-related TEAEs that were fatal or life-threatening. The nature and incidence rates of AEs observed with CVC were similar to those observed with placebo, except for nausea, elevation in transaminases, and nephrolithiasis, the latter, a finding inconsistent with previous safety data. The proportion of participants who experienced DILI (cases adjudicated as possible or probable DILI) was higher in the CVC group (4 participants [0.3%]) compared to placebo group (0 participants [0%]), suggesting a possible causal relationship between CVC and DILI. Nevertheless, all these cases were non-serious, non-clinically significant, and reversible after CVC discontinuation.

ROLLOVER (Study 3152-201-002)

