6.3.5 Laboratory Evaluations

At screening, pre-entry, and entry, all protocol-required laboratory values must be recorded regardless of grade.

For post-entry assessments, record all of the following values regardless of grade:

- Hemoglobin
- White blood cell (WBC) count with differential
- Platelet count
- Creatinine
- Fasting glucose
- HbA1c
- Total cholesterol (fasting)
- HDL cholesterol (fasting)
- LDL cholesterol (fasting)
- Triglycerides (fasting)
- AST
- ALT
- Total bilirubin
- Direct bilirubin
- Prothrombin Time (PT)
- International Normalized Ratio (INR)
- Estimated GFR

NOTE: Refer to the A5415 MOPS for the link to the CKD-Epi equation and calculator.

Refer to [section 7.2](#) for AE reporting requirements for post-entry abnormal laboratory findings.

Refer to the current A5415 Laboratory Processing Chart (LPC) for the collection and processing instructions.

Fasting Instructions

Fasting is defined as nothing to eat or drink except prescription medications and water for at least 8 hours, preferably 10 hours. If participants are in a non-fasting state, they should be instructed to return to the clinic within 3 days of the original scheduled visit for fasting evaluations (as indicated in [section 6.1](#)).

Fasting is NOT required for pregnant participants.

For the fasting requirements for the FDG-PET/CT imaging: See [section 6.3.9](#).

Hematology

Hemoglobin, hematocrit, red blood cells (RBCs), WBCs with differential, absolute neutrophil count (ANC), and platelets

Blood Chemistries

Serum electrolytes (sodium, potassium, and chloride), BUN, creatinine, and amylase.

Fasting Glucose

Fasting blood sample for glucose will be collected per [section 6.1](#). **All glucose collections** should be collected in a gray top tube (sodium fluoride). Refer to the current A5415 LPC for the collection and processing instructions.

Insulin

At screening, fasting blood sample for insulin will be collected and insulin testing will be performed in real time.

After screening, insulin testing will be performed on stored serum (see [sections 3.0](#) and [6.3.8](#)).

Fasting Lipid Panel

Total cholesterol, HDL cholesterol, LDL cholesterol, and triglycerides

Liver Function Tests (LFTs)

AST (SGOT), ALT (SGPT), alkaline phosphatase (ALP), total bilirubin, and direct bilirubin

HbA1C

HbA1c will be done in real-time per [section 6.1](#).

Prothrombin Time (PT) and International Normalized Ratio (INR)

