8.2 Specific Management of Toxicities Related to Study-Provided Treatment

8.2.1 Elevated Liver Enzymes

Site personnel must report treatment-emergent (i.e., not present at screening or baseline) and confirmed ALT and/or AST elevations meeting any of the following criteria for suspected drug-induced liver injury (DILI), with special consideration given to baseline transaminase values:

- When the baseline ALT or AST values are $<2 \times$ ULN, and the ALT and/or AST increases to $>3 \times$ ULN and $>5 \times$ the baseline value (confirmed upon repeat testing).

- When the baseline ALT or AST values are $<2 \times$ ULN, and ALT and/or AST increases to $>3 \times$ ULN but $\leq 5 \times$ the baseline value (confirmed upon repeat testing) AND the increase is accompanied by total bilirubin $>2 \times$ ULN (in participants with Gilbert's syndrome use direct bilirubin $>2 \times$ baseline) AND/OR if the participant also has symptoms consistent with clinical hepatitis (for example, fatigue, nausea/vomiting, right upper quadrant [RUQ] abdominal pain or tenderness, fever, rash, or eosinophilia) without an alternative explanation for the event as judged by the site investigator.
- When the baseline values are $\geq 2 \times$ ULN but $<5 \times$ ULN, and the ALT and/or AST increases to $>3 \times$ the baseline value (confirmed upon repeat testing).
- When the baseline values are $\geq 2 \times$ ULN but $<5 \times$ ULN, and the ALT and/or AST increases to $>2 \times$ the baseline but $\leq 3 \times$ baseline value (confirmed upon repeat testing) AND the increase is accompanied by total bilirubin $>2 \times$ ULN (in participants with Gilbert's syndrome use direct bilirubin $>2 \times$ baseline) AND/OR if the participant also has symptoms consistent with clinical hepatitis (e.g., fatigue, nausea/vomiting, RUQ abdominal pain or tenderness, fever, rash, eosinophilia) without an alternative explanation for the event as judged by the site investigator.
- When baseline values are $\geq 5 \times$ ULN and ALT and/or AST increases to $>2 \times$ the baseline value (confirmed upon repeat testing).
- When the ALT and/or AST increases to $>3 \times$ ULN and $>2 \times$ baseline (confirmed upon repeat testing) AND the increase is accompanied by either total bilirubin increase to $>2 \times$ the baseline value OR INR increase by >0.3 from baseline to a value >1.5 .

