10.6.3 Secondary Analyses

A sensitivity analysis for the primary analysis will include participants in the per-protocol analysis described in the primary analysis above as well as participants with data available for evaluation completed at premature treatment or study discontinuation that is after week 12 as long as they are on treatment within 7 days of the evaluation.

Supplementary analyses for the primary analysis will exclude participants with confirmed HIV-1 RNA >200 copies/mL at any time during the course of the study and extensive periods of ART interruption (see SAP for more detail).

Key secondary endpoints ([section 10.2.2](#)) will be analyzed in the same manner (also per-protocol) as in the primary analysis.

For immunology markers, two blood draws will be performed at baseline (pre-entry and entry) and week 22/24 (week 22 and week 24) and the measurements will be the average of two values in order to reduce intra-participant variability. Outcome measurements may be transformed for analyses on the \log_{10} scale, as appropriate.

Safety will be evaluated by summarizing the nature and rate of AEs (signs and symptoms, laboratory values, SAEs) for the safety analysis population.

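### SAP 6.1 lists renal laboratory values over time but plans no ALT/AST/bilirubin output and no by-arm count of participants meeting the protocol's suspected-DILI criteria

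*SAP*

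**What the plan says.** Protocol 2.1 describes the hepatic findings of the phase 3 NASH study (AURORA): "alanine aminotransferase increase (45 [3.8%] participants in the CVC group versus 9 [1.5%] participants in the placebo group") and "aspartate aminotransferase increase (38 [3.2%] participants in the CVC group versus 6 [1.0%] participants in the placebo group"). It adds four cases adjudicated as possible or probable DILI on CVC against none on placebo, reads this as a possible causal link, and then qualifies it: "Nevertheless, all these cases were non-serious, non-clinically significant, and reversible after CVC discontinuation".

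The trial is set up to watch the liver. The schedule in Protocol 6.1 has liver tests at entry and weeks 4, 12 and 24. Protocol 6.3.5 says "For post-entry assessments, record all of the following values regardless of grade", and its list includes AST, ALT, and total and direct bilirubin. Protocol 8.2.1 opens with "Site personnel must report treatment-emergent (i.e., not present at screening or baseline) and confirmed ALT and/or AST elevations meeting any of the following criteria" and sets out six criteria for suspected DILI.

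For analysis, Protocol 10.6.3 says "Safety will be evaluated by summarizing the nature and rate of AEs (signs and symptoms, laboratory values, SAEs) for the safety analysis population". SAP 6.1 turns this into five outputs on the Safety set:

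1. a table of all new AEs by preferred term within system organ class;
2. "Listing of longitudinal creatinine and eGFR with creatinine-related AEs";
3. a table or listing of SAEs;
4. a listing of treatment-related AEs;
5. a table or listing of AEs related to PET/CT.

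Listings carry grade, action taken and relationship. The tables are N (%), and no grade is named. No other SAP section displays liver enzymes or bilirubin, and none refers to the 8.2.1 criteria. APRI and FIB-4 are an exploratory objective (SAP 2.3.3) but have no entry among the outcome measures in SAP 3.3.

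**The concern.** Safety is a secondary objective, and transaminase elevation is one of the differences from placebo that the protocol itself singles out. The SAP gives renal function a listing of values over time and gives the liver nothing comparable, although the values are on the eCRF and the protocol defines what counts as a suspected case.

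The case most easily lost is the kind already seen on this drug: non-serious and reversible. If the site also judges it unrelated, it drops out of both the SAE output and the related-AE listing. It is then one unit in a preferred-term count, where an isolated moderate ALT rise and a rise accompanied by raised bilirubin look the same. The report could not say how many participants in each arm met the protocol's own criteria.

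**Working it through.** **Step 1. Reproduce the prior-study figures.** Counts are from Protocol 2.1; denominators (1180 CVC, 589 placebo) are from Protocol Appendix I.

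| Event | CVC | Placebo |
|---|---|---|
| ALT increase | 45/1180 = 3.81% | 9/589 = 1.53% |
| AST increase | 38/1180 = 3.22% | 6/589 = 1.02% |
| Adjudicated DILI | 4/1180 = 0.34% | 0/589 = 0% |

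All agree with the stated percentages. Two-sided Fisher p-values are 0.008 (ALT), 0.005 (AST) and 0.31 (DILI). The enzyme excess is clear; the DILI difference rests on four cases.

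**Step 2. Follow one case through the SAP.** Take a confirmed 8.2.1 case that is non-serious and judged unrelated to study drug.

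| SAP output | What it would show |
|---|---|
| 6.1 item 1, all AEs | One count under a preferred term, by arm, no grade |
| 6.1 item 2, renal listing | Nothing |
| 6.1 item 3, SAEs | Nothing (non-serious) |
| 6.1 item 4, related AEs | Nothing (judged unrelated) |
| 6.1 item 5, PET/CT AEs | Nothing |
| 3.3 secondary outcome 7, treatment-limiting AE | May be counted, not organ-specific |
| 5.7, interruption and discontinuation reasons | May appear under a reason, not linked to 8.2.1 |

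The last two rows are live because Protocol 8.2.1 calls for treatment to be interrupted on confirmation, and Protocol 7.2 collects AEs that change treatment at any grade. So the case is counted by arm, but no output shows its grade or that it met 8.2.1.

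**Step 3. Ask whether 8.2.1 status can be recovered from those outputs.** All six criteria use the participant's own baseline. Three also need concurrent bilirubin, INR or symptoms. Protocol 4.1.7 admits ALT and AST up to 5 times ULN. As an illustration, a participant starting at 2.5 times ULN meets the third criterion only above 3 × 2.5 = 7.5 times ULN, and the fourth between 2 × 2.5 = 5 and 7.5 times ULN when bilirubin is also raised or there are symptoms of hepatitis without another explanation. A preferred-term count contains none of this.

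**Step 4. Expected size in this trial.** Final enrolment is 110 (SAP 2.1). The split by arm is not given; 2:1 implies 110 × 2/3 ≈ 73 and 110/3 ≈ 37. Expected events = arm size × prior rate.

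- ALT: 73 × 45/1180 = 2.8; 37 × 9/589 = 0.6.
- AST: 73 × 38/1180 = 2.4; 37 × 6/589 = 0.4.
- DILI on CVC: 73 × 4/1180 = 0.25; P(at least one) = 1 − (1 − 4/1180)^73 = 22%.

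At the planned 62/31 the figures are 2.4 versus 0.5 for ALT, 0.21 DILI cases, and 19%. If no DILI case occurs among 73, the one-sided 95% upper bound is 1 − 0.05^(1/73) = 4.0%, about 12 times the phase 3 rate of 0.34%. Counts of this size can be described but not usefully tested.

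**The case against.** The best reply is that the SAP already carries hepatic events. Protocol 7.2 records every laboratory finding of Grade 2 or higher as an AE, so these reach the preferred-term table. Everything after SAP 5.4 is by treatment group unless stated otherwise. Related AEs, and SAEs where listed, come with grade. This stands. A reader might infer that DILI would go unreported by arm, or that hepatic events would appear only as ungraded counts; the documents support neither.

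A reader might also see Protocol 10.6.3 as promising a summary of laboratory values that the SAP then omits. In that sentence laboratory values are one kind of AE, and SAP 6.1 item 1 tabulates all new AEs. There is no conflict between the documents.

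Nor do the documents support the idea that the recorded enzyme values would supply a well-powered between-arm test. They give no SD for log ALT, and nothing links an excess in event rates to a shift in the mean; an excess confined to a few participants would barely move it.

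Two further points limit the weight of the finding. SAP 1.1 leaves more detailed table and figure outlines to an Analysis Implementation Plan that is not among the documents and may add liver tables. During the trial, the monitoring committee sees AEs by arm (Protocol 10.5) and the clinical management committee is told of confirmed suspected DILI within 48 hours (Protocol 8.2.1). Neither of these monitoring arrangements puts an 8.2.1 count in the final report.

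**Conclusion.** The gap is real but limited to descriptive safety reporting. The SAP has no ALT/AST/bilirubin output and no by-arm count of participants meeting 8.2.1, for an organ where the protocol reports an excess on the study drug and where the data are already required. A non-serious case judged unrelated would be counted by arm, but its grade, multiple of baseline and concurrent bilirubin would not be shown.

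The numbers at stake are small: about 3 ALT events and a 22% chance of any DILI case on CVC. These assume a 73/37 split with everyone treated, and that phase 3 NASH incidence carries over to 24 weeks in people with HIV. It is probably too high for 24 weeks, because the phase 3 histology endpoint alone was at Month 12. With so few cases, what helps the reader is to see each one in full. This is a cheap improvement to the SAP and has no bearing on the primary analysis.

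**What to change.** Add to SAP 6.1, on the Safety set and by arm:

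1. N (%) and a listing of participants meeting any Protocol 8.2.1 criterion, whatever the seriousness or attribution, with ALT, AST and bilirubin over time for those participants (and INR where measured, since one criterion uses it). This parallels the creatinine/eGFR listing. State the source: the laboratory parts can be derived from recorded values, but the symptom parts need the sites' reports, because Protocol 7.2 in general records signs and symptoms only from Grade 3.
2. Maximum grade in the all-AE table.

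Present both descriptively, without tests. Tables by multiple of ULN or baseline, a plot of maximum ALT against maximum bilirubin, and adjusted contrasts of log ALT are optional.

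The cost is SAP wording and a small amount of programming, with no new visits or assays. The downside is a few more safety outputs without multiplicity control. Clinical management and the primary analysis do not change.
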